#### HBV genotyping and HBV sequencing

HBV genotyping and HBV sequencing will be summarised descriptively using frequency count and percentage by study cohort. Emergence of HBV mutations (sequencing of ARO-HBV target site, Core/pre-core, HBsAg epitope, NUC resistant mutations any other mutations by deep sequencing) will be summarized accordingly, depending on the available HBV mutation data. It should be noted that the HBV sequencing data could be missing for HBeAg negative subjects and subjects on NUCs, as they may have HBV DNA that is too low to sequence.

#### Quantitative assessments: HBV DNA, qHBsAg, qHBeAg, qHBcrAg, qHBV RNA, anti-HBsAg and ratio of bound/free anti-HBsAg (if available)

Quantitative HBV DNA, qHBsAg (overall and by IL28B genotype mutation [rs12979860 and rs8099917]), qHBeAg qHBcrAg and qHBV RNA will be logarithm (log 10) transformed, and the observed log transformed value and change from baseline of the log transformed value will be summarised descriptively for all time points assessed. In addition, for HBV DNA, qHBsAg, qHBeAg, qHBcrAg, and qHBV RNA, the change to the maximum post-dose decline (nadir) from baseline will be pooled for a nadir 'visit' and summarized by cohort as well. The nadir values will also be calculated based on the overall study period (including the follow-up visits). The ratio of bound/free anti-HBsAg will be summarized descriptively without log transformation. The change from baseline values at each post-baseline visit will also be categorized ('<0.5 log decline', '0.5-<1.5 log decline', '1.5-< 3 log decline', '> 3 log decline') and summarized. Only patients with a baseline result above the LLQ for the specific parameter will be included in the post-baseline summaries.

The summary table will also be repeated for the following subgroups (based on the categories described for the qualitative assessments below):

- Baseline HBV DNA:
  - Baseline HBV DNA Not Detected
  - Baseline HBV DNA Detected

- Baseline HBeAg:
  - Baseline qHBeAg Negative
  - Baseline qHBeAg Positive

The quantitative HBV DNA, qHBsAg, qHBeAg, qHBcrAg and qHBV RNA over time (up to Day 113) will be plotted for mean and individual subject values, based on log transformed data, by cohort. The log transformed results will be plotted on a linear scale (y-axis). The log transformed LLQ values will be added as a horizontal reference line. The change from baseline values will also be presented. The plots will also be presented for the subset of CHB patients that participated in the follow-up period and will include all available data. Only patients with a baseline result above the LLQ for the specific parameter will be included in the plots.

Qualitative assessments: HBV DNA, HBV RNA, HBsAg Loss, anti-HBsAg, HBeAg and anti-HBeAg

The quantitative HBV DNA results will be categorized as follows for the qualitative HBV DNA summary:

- Target Detected: All results that are equal to or above the LLQ cut-off value and results below the LLQ that have been classified as 'Detected' (for example, '<15 Detected', '< 20 Detected', etc.) by the analyzing laboratory.
- Target Not Detected: Results below the LLQ cut-off values that have been classified as 'Not Detected' by the analyzing laboratory.

The HBV RNA interpretation provided by the analyzing laboratory will be categorized as follows for the qualitative HBV RNA summary:

- Target Detected: All results where the interpretation provided by the analyzing laboratory is 'Positive' or 'LLOQ'.
- Target Not Detected: All results where the interpretation provided by the analyzing laboratory is 'Negative'.

Loss of HBsAg ('Not Detected') is defined as HBsAg of less than 0.05 IU/mL. Post-baseline qHBsAg results will be classified as follows for the qualitative HBsAg summary:

- Loss of HBsAg: Reported qHBsAg result is below the LLQ cut-off value.
- HBsAg Present: Reported qHBsAg result is equal to or above the LLQ cut-off value.

The qualitative HBeAg results will be categorized as follows for the qualitative HBeAg summary:

- Positive: Qualitative results reported as 'Detected' by the analyzing laboratory.
- Negative: Qualitative results reported as 'Not Detected' by the analyzing laboratory.

Anti-HBsAg and anti-HBeAg will be reported as 'Detected' or 'Not Detected' by the analyzing laboratory. Anti-HBsAg and anti-HBeAg will only be assessed if there was a HBsAg or HBeAg loss during the study and may not be available at all timepoints.

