### Data Handling Rules

The units and lower limit of quantitation (LLQ) cut-off and imputed values in the table below will be used in all derivations and outputs.

Parameter	Qualitative / Quantitative	LLQ	Unit	Values for Imputation		
				< LLQ	< LLQ Detected	< LLQ Not Detected
HBeAg	Qualitative	0.22	PEIU/mL	N/A	N/A	N/A
qHBeAg	Quantitative	0.11	PEIU/mL	0.055	0.055	0.055 a)
HBV DNA	Quantitative	20	IU/mL	N/A	15	5
HBV RNA	Quantitative	1.65	Log10 U/mL	N/A	0.825	0.4125
qHBcrAg	Quantitative	1	kU/mL	0.5	N/A	N/A
qHBsAg	Quantitative	0.05	IU/mL	0.025	N/A	N/A

a) Values below 0.11 PEIU/mL may have been reported as 'not detected'

All reported qHBsAg and qHBcrAg results below the LLQ cut-off values will be treated as below LLQ and included in the '< LLQ' category counts.

qHBeAg results will be imputed based on the reported HBeAg (qualitative) results provided by the analyzing laboratory:

- Positive: All reported qHBeAg results equal to or above the LLQ cut-off value (0.11 PEIU/mL)
- '< LLQ': All results below the LLQ cut-off value where the HBeAg result is any outcome other than 'Not Detected'
- Negative: All results below the LLQ cut-off value where the HBeAg result is 'Not Detected'

HBV DNA results reported as 'Not Detected' will be imputed as 5 IU/mL. Results reported as 'Detected' or results below the LLQ cut-off value where the status is not specified ('Detect' or 'Not Detected') will be imputed as 15 IU/mL.

The quantitative HBV RNA results will be imputed based on the HBV RNA interpretation provided by the analyzing laboratory. If the interpretation is reported as 'LLOQ' and the result is below the LLQ cut-off value, the result will be imputed as 0.825 Log10 U/mL. Interpretations

reported as 'Negative' or results below the LLQ cut-off value where the status is not specified ('LLOQ' or 'Negative') will be imputed as 0.4125 Log10 U/mL.

Screening and baseline results below LLQ will not be imputed for any of the parameters and patients with results below the LLQ value at baseline will not be included in any of the post-dose summaries or the figures for the specific parameter.

Results equal to or above the LLQ cut-off value will be analyzed as reported, except where the result has been reported as a range ('> x' or '< y') in which case the result will be imputed to one significant digit above or below the reported cut-off value (i.e., '<30' will be analyzed as 29 and '>30.0' will be analyzed as 30.1).

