All results (except for HBV RNA) will be log transformed (base 10) for analysis purposes.

Imputed results will be identified in the data listings.

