14.2.4.2	Scatterplot of Individual and Mean Plasma Dose Normalized AUC 0-inf versus Dose for ARO-HBV	PK	X
14.2.4.3	Scatterplot of Individual and Mean Plasma Dose Normalized AUC 0-t versus Dose for ARO-HBV	PK	X
14.2.4.4	Scatterplot of Individual and Mean Plasma Dose Normalized C max versus Dose for ARO-HBV	PK	X
14.2.5.1	Mean (+/-SD) of Creatinine versus Time by Cohort	Safety	X
14.2.5.2	Mean (+/-SD) of Creatine Kinase versus Time by Cohort	Safety	X
14.2.5.3	Mean (+/-SD) of AST versus Time by Cohort	Safety	X
14.2.5.4	Mean (+/-SD) of ALT versus Time by Cohort	Safety	X
14.2.5.5	Mean (+/-SD) of Total Bilirubin versus Time by Cohort	Safety	X
14.2.6.1.1	Mean (+/-SD) of Logarithm Transformed Quantitative HBV DNA versus Time by Cohort [CHB cohorts only]	PD	X
14.2.6.1.2	Mean (+/-SD) Change from Baseline in Logarithm Transformed Quantitative HBV DNA versus Time by Cohort [CHB cohorts only]	PD	X
14.2.6.2.1	Mean (+/-SD) of Logarithm Transformed Quantitative HBsAg versus Time by Cohort [CHB cohorts only]	PD	X
14.2.6.2.2	Mean (+/-SD) Change from Baseline in Logarithm Transformed Quantitative HBsAg versus Time by Cohort [CHB cohorts only]	PD	X
14.2.6.3.1	Mean (+/-SD) of Logarithm Transformed Quantitative HBeAg versus Time by Cohort [CHB cohorts only]	PD	X
14.2.6.3.2	Mean (+/-SD) Change from Baseline in Logarithm Transformed Quantitative HBeAg versus Time by Cohort [CHB cohorts only]	PD	X
14.2.6.4.1	Mean (+/-SD) of Logarithm Transformed Quantitative HBcrAg versus Time by Cohort [CHB cohorts only]	PD	X
14.2.6.4.2	Mean (+/-SD) Change from Baseline in Logarithm Transformed Quantitative HBcrAg versus Time by Cohort [CHB cohorts only]	PD	X
14.2.6.5.1	Mean (+/-SD) of Logarithm Transformed Quantitative HBV RNA versus Time by Cohort [CHB cohorts only]	PD	X

No.	Title	Analysis Population	Day 113: Interim Analysis
14.2.6.5.2	Mean (+/-SD) Change from Baseline in Logarithm Transformed Quantitative HBV RNA versus Time by Cohort [CHB cohorts only]	PD	X
14.2.7.1.1	Individual Logarithm Transformed Quantitative HBV DNA versus Time by Cohort [CHB cohorts only]	PD	X
14.2.7.1.2	Individual Change from Baseline in Logarithm Transformed Quantitative HBV DNA versus Time by Cohort [CHB cohorts only]	PD	X
14.2.7.2.1	Individual Logarithm Transformed Quantitative HBsAg versus Time by Cohort [CHB cohorts only]	PD	X

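### The SAP has two conflicting rules for HBV RNA: one analyses it as reported in log10 U/mL, the other, read literally, takes a second log

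*SAP*

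**What the plan says.** The Data Handling Rules in SAP section 11 tabulate HBV RNA with an LLQ of "1.65 Log10 U/mL". For a result below the LLQ that the laboratory interprets as LLOQ, "the result will be imputed as 0.825 Log10 U/mL". Negative results, and results below the LLQ with no stated status, "will be imputed as 0.4125 Log 10 U/mL". The scope of that table is wide: "The units and lower limit of quantitation (LLQ) cut-off and imputed values in the table below will be used in all derivations and outputs". The rules close with an exemption: "All results (except for HBV RNA) will be log transformed (base 10) for analysis purposes".

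The Quantitative assessments part of the same section defines the outputs: observed values, change from baseline, nadir, decline categories and plots. Its list of markers includes HBV RNA: "qHBeAg qHBcrAg and qHBV RNA will be logarithm (log 10) transformed". The only marker it leaves untransformed is the bound/free anti-HBsAg ratio. For the plots it adds "The log transformed LLQ values will be added as a horizontal reference line", with no exception for RNA.

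Section 7.1 also places HBV RNA in a list introduced as log-transformed baseline values. A figure title in section 21 reads "Mean (+/-SD) of Logarithm Transformed Quantitative HBV RNA versus Time by Cohort".

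**The concern.** A result in log10 U/mL needs no further log: its change from baseline is already a log reduction. The general rule says this, but the paragraph a programmer would open to build the HBV RNA tables and plots says the opposite. The decline categories there (cut at 0.5, 1.5 and 3 log) make sense only for a single log.

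Reduction in HBV RNA, with ARO-HBV alone or combined with JNJ-6379, is a stated exploratory measure of activity (Protocol section 5.3, SAP section 2.2.3). A second log would shrink the reductions, put patients in the wrong category, and leave RNA on a different scale from HBsAg, HBeAg, HBcrAg and HBV DNA in the same tables.

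**Working it through.** The plan gives no HBV RNA effect size to reproduce, and no RNA baseline or nadir for this trial. The check is therefore a comparison of the two rules over assumed values.

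**Inputs from the SAP (section 11, Data Handling Rules):** LLQ 1.65; imputed values 0.825 and 0.4125; all in log10 U/mL. Only patients with a baseline above the LLQ enter the post-baseline summaries.

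**Formulas.** With baseline b and post-dose value n, both in log10 U/mL:
- as reported (exemption applied): fall = b − n
- logged again (output paragraph read literally): fall = log10(b) − log10(n)

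**A true 4-log fall, over assumed pairs:**

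| b | n | b − n | log10(b) − log10(n) |
|---|---|---|---|
| 4.4125 | 0.4125 (imputed) | 4.0 | 1.029 |
| 4.825 | 0.825 (imputed) | 4.0 | 0.767 |
| 5.65 | 1.65 (LLQ) | 4.0 | 0.535 |
| 6 | 2 | 4.0 | 0.477 |
| 7 | 3 | 4.0 | 0.368 |
| 8 | 4 | 4.0 | 0.301 |
| 9 | 5 | 4.0 | 0.255 |

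For the fourth row: log10(6) − log10(2) = 0.778 − 0.301 = 0.477. As reported, every row falls in the category above 3 log. Logged again, every row falls in one of the two lowest categories. The shrinkage grows with baseline, so cohorts with different baseline RNA could not be compared.

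**A lower assumed baseline.** From 3 to the imputed 0.825, the true fall is 3 − 0.825 = 2.175. Logged again it is 0.561. The category changes from 1.5 to under 3 log, to 0.5 to under 1.5 log.

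**Reach of the categories.** The lowest possible post-dose value is 0.4125. A double-logged fall reaches 1.5 only if b ≥ 0.4125 × 10^1.5 = 13.0 log10 U/mL. It reaches 3 only if b ≥ 0.4125 × 10^3 = 412.5 log10 U/mL. The two largest categories would be empty in practice.

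**Reference line and imputed values.** log10(1.65) = 0.217, log10(0.825) = −0.084 and log10(0.4125) = −0.385. Logged again, the LLQ line would sit at 0.22 instead of 1.65, and imputed results would plot below zero.

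**The case against.** The best reply is that the SAP, read as a whole, already has the right rule. The exemption names HBV RNA alone and looks deliberate, while the output paragraph is a generic list of five markers. The handling table applies to every derivation and output, and a log of a log is not in log10 U/mL, so a second log would breach the table as well as the exemption. On this view, log transformed in the output paragraph only means analysed on the log10 scale. Section 7.1 is loose too: its list also contains genotype, which cannot be logged. The figure titles are true of a value already in log10.

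Much of this stands. It shows which rule is correct, and it makes section 7.1 and the figure titles weak evidence of a separate instruction. It does not remove the conflict. The output paragraph says the markers will be transformed, makes its own exception for the bound/free ratio, and leaves RNA on the list. It then asks for transformed LLQ values, although the RNA limit is already a log.

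A reader might go further and infer that the SAP prescribes double logging, so that a 4-log fall will appear as about 0.5. The documents do not support that, because the exemption says the reverse. The 0.5 also holds only for baselines near 5.7 to 6 with a nadir at or just above the LLQ. Protocol section 4.4 describes baseline HBV RNA in a JNJ-6379 study as generally low and sometimes undetectable, which is a further reason to treat the 4-log fall as an illustration.

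**Conclusion.** The two instructions conflict, and the output paragraph is wrong as written. The consequence is conditional. Only if that paragraph were followed and the exemption ignored would a true 4-log fall be tabulated as roughly 0.26 to 1.03, with the top two decline categories practically unreachable. The range rests on the assumed pairs shown. The statement about categories rests only on the SAP's lowest imputed value and on baselines staying below 13 log10 U/mL.

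It should not be inferred that RNA results already produced are wrong. HBV RNA tables and figures are marked for the Day 113 interim, and SAP section 17.2 says that analysis was completed in February 2020, but the documents do not say which rule was programmed. The current SAP cites a protocol dated 28 February 2020, so the interim may have been run under SAP text that is not among the documents.

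Severity is moderate. HBV RNA is exploratory and qualified by feasibility, the analyses are descriptive, and by-subject listings keep the results traceable. The primary safety objective and the secondary HBsAg objective are untouched.

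**What to change.** - In the Quantitative assessments part of SAP section 11, and in section 7.1, take qHBV RNA out of the list of markers to be transformed. Add: *HBV RNA is reported in log10 U/mL and is analysed as reported; change = post-baseline minus baseline.*
- State that the HBV RNA reference line is drawn at 1.65.
- Check which rule was programmed for the HBV RNA tables and figures in the February 2020 interim, and rerun them if a second log was taken.
- Retitling Figures 14.2.6.5.1–2 and 14.2.7.5.1–2 is optional, provided logarithm transformed is understood to mean the reported log10 value.

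The cost is a few words in the SAP and one programming check. No new data are needed and trial conduct does not change.

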## 19. TABLES

Tables will be produced separately for NHV cohorts (Cohorts 1, 2, 3, 4 and 5), CHB cohorts (Cohorts 1b, 1c, 2b, 3b, 4b, 5b, 6, 7, 8, 9, 10, 11 and 12), and the subset of CHB patients that participated in the follow up period.

No.	Title	Analysis Population	Day 113: Interim Analysis
14.1.1.1	Summary of Disposition	Safety	X
14.1.1.2	Summary of Demographics	Safety	X
14.1.1.3.1	Summary of Baseline Disease Characteristics	Safety	X
14.1.1.3.2	Summary of Baseline Virology Characteristics	PD	X
14.2.1.1	Summary of Plasma Concentrations of ARO-HBV (ng/mL) by Dose [NHV Cohorts 1, 2, 3, 4 and 5 only]	PK	X
14.2.2.1	Summary of Plasma Pharmacokinetic Parameters of ARO-HBV by Dose [NHV Cohorts 1, 2, 3, 4 and 5 only]	PK	X
14.2.2.2	Analysis of Dose Proportionality for ARO-HBV [NHV Cohorts 1, 2, 3, 4 and 5 only]	PK	X
14.2.3.1	Summary of Plasma Concentrations of ARO-HBV (ng/mL), Nucleos(t)ide and JNJ-6397 Plasma Concentrations (Cohort 12) [CHB Cohort 12 only]	PK	
14.2.4.1	Summary of Anti-drug Antibodies [CHB cohorts only]	Safety	
14.2.4.2.1	Summary of Quantitative HBV Assessments and Change from Baseline [CHB cohorts only]	PD	X
14.2.4.2.1.1	Summary of Quantitative HBV Assessments and Change from Baseline by Baseline HBV DNA Group [CHB cohorts only]	PD	X
14.2.4.2.1.2	Summary of Quantitative HBV Assessments and Change from Baseline by Baseline HBeAg Group [CHB cohorts only]	PD	X
14.2.4.2.2	Summary of Quantitative HBsAg (IU/mL) by IL28B Genotype and Change from Baseline [CHB cohorts only]	PD	
14.2.4.2.3	Summary of Quantitative HBV Assessments Change from Baseline Categories [CHB cohorts only]	PD	X
14.2.4.2.4	Summary of Qualitative HBV Assessments [CHB cohorts only]	PD	X
14.2.4.3	Summary of HBV Virology Response [CHB cohorts only]	PD	X
14.2.4.4	Summary of Time to HBsAg Loss [CHB cohorts only]	PD	X
14.2.4.5	Summary of Time to Anti-HBsAg Seroconversion [CHB cohorts only]	PD	X
14.2.4.6	Summary of Duration of Response for HBV DNA [CHB cohorts only]	PD	X
14.2.4.7	Summary of Duration of Response for HBsAg	PD	X

No.	Title	Analysis Population	Day 113: Interim Analysis
	[CHB cohorts only]		
14.2.4.8	Summary of Duration of Response for HBeAg [CHB cohorts only]	PD	X
14.2.4.9	Summary of Duration of Response for HBcrAg [CHB cohorts only]	PD	X
14.2.4.10	Summary of Duration of Response for HBV RNA [CHB cohorts only]	PD	X

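### The log-decline categories in SAP Table 14.2.4.2.3 have no place for a decline of exactly 3 log, count rises as small declines, and do not show which results are capped by the assay limit

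*SAP*

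**What the plan says.** SAP section 11, under Quantitative assessments, states that the change from baseline at each post-baseline visit will "also be categorized ('<0.5 log decline', '0.5-<1.5 log decline', '1.5-< 3 log decline', '> 3 log decline') and summarized". The output is Table 14.2.4.2.3 in SAP section 19, titled "Summary of Quantitative HBV Assessments Change from Baseline Categories". Entry to it is restricted: "Only patients with a baseline result above the LLQ for the specific parameter will be included in the post-baseline summaries".

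The Data Handling Rules in the same section fix the value used when a post-baseline result is below LLQ. For HBV DNA the row reads "HBV DNA Quantitative 20 IU/mL N/A 15 5" (LLQ, unit, then the values for the below-LLQ, below-LLQ detected and not-detected columns), and the text repeats that "HBV DNA results reported as 'Not Detected' will be imputed as 5 IU/mL". The other rows, giving LLQ and then imputed value, are "qHBeAg Quantitative 0.11 PEIU/mL 0.055 0.055", "qHBcrAg Quantitative 1 kU/mL 0.5" and "qHBsAg Quantitative 0.05 IU/mL 0.025". HBV RNA has an LLQ of 1.65 on the log10 scale, with imputed values of 0.825 (below LLQ) and 0.4125 (negative).

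The Data Handling Rules also mention counts of qHBsAg and qHBcrAg results below LLQ, but assign them to no table. The category list has no row for them.

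**The concern.** A categorical table should place every patient in exactly one row, under a label that describes what happened. Here the two middle categories include their lower limits, but the top one excludes 3, so 3.0 belongs nowhere. The bottom category has no lower limit, so a patient whose marker rises tenfold sits beside one whose marker fell slightly, under a label that says decline.

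The fixed imputed values add a third problem. Once a result is below LLQ, the recorded decline depends only on the baseline. A cohort's distribution over the categories therefore reflects its baseline levels as well as the treatment effect, and the table does not show which entries are capped. This matters because most cohorts enrol regardless of HBeAg or NUC status, and SAP section 11 itself expects HBV DNA too low to sequence in some HBeAg-negative and NUC-treated patients.

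**Working it through.** The plan gives no figure of its own to reproduce, so the check applies its categories to its imputed values.

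**Inputs.** LLQ and imputed values: SAP section 11, Data Handling Rules. HBsAg entry minimum of 5 IU/mL at screening: protocol section 7.2, CHB inclusion criterion 11. Cohort sizes: SAP section 2.4.

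**Formulas.** Decline = log10(baseline / imputed value). For HBV RNA, already on the log10 scale, it is a plain difference. A below-LLQ result falls in the lowest category when baseline < imputed value × 10^0.5 (× 3.162). It scores above 3 log only when baseline > imputed value × 1,000.

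| Marker and result | Imputed | Decline if baseline equals LLQ | Lowest category when baseline is | Above 3 log needs baseline over |
|---|---|---|---|---|
| HBV DNA, below LLQ, detected | 15 | log10(20/15) = 0.12 | 20 to <47.4 IU/mL | 15,000 |
| HBV DNA, not detected | 5 | log10(20/5) = 0.60 | never | 5,000 |
| qHBeAg | 0.055 | log10(0.11/0.055) = 0.30 | 0.11 to <0.174 PEIU/mL | 55 |
| qHBcrAg | 0.5 | log10(1/0.5) = 0.30 | 1.0 to <1.58 kU/mL | 500 |
| qHBsAg | 0.025 | log10(0.05/0.025) = 0.30 | <0.079 IU/mL, far below the entry minimum | 25 |
| HBV RNA, below LLQ | 0.825 | 1.65 − 0.825 = 0.825 | never | 3.825 (log10) |
| HBV RNA, negative | 0.4125 | 1.65 − 0.4125 = 1.2375 | never | 3.4125 (log10) |

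**Examples for the lowest category.** HBV DNA 40 to 15: 0.43. HBcrAg 1.5 to 0.5: 0.48. HBeAg 0.15 to 0.055: 0.44.

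**Ceiling for HBsAg loss.** From 5 IU/mL, log10(5/0.025) = 2.30. From any baseline of 5 to <25 IU/mL, loss is recorded as 1.5 to <3 log.

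**Exactly 3 log.** HBsAg 25 to 0.025, HBcrAg 500 to 0.5, HBV DNA 5,000 to 5 and HBV DNA 15,000 to 15 all give 3.00. So does an ordinary measured pair such as HBsAg 1,000 to 1. None meets any of the four definitions.

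**Increase.** HBsAg 1,000 to 10,000 is a decline of −1.0. The only definition it satisfies is the one for under 0.5 log.

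**Weight of one patient.** 1/12 = 8.3 percentage points in Cohort 12 and 1/4 = 25 points in a cohort of four. It is more where the baseline rule removes patients from the denominator.

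**The case against.** The strongest reply is that the floor is handled elsewhere. Section 11 provides detected/not-detected summaries for HBV DNA and HBV RNA, HBsAg loss and HBeAg status (Table 14.2.4.2.4), response rates with exact intervals (Table 14.2.4.3), and time to HBsAg loss (Table 14.2.4.4). Increases can be seen in the minimum and maximum of the change from baseline, in the individual change plots and in the listings. Exactly 3.0 log needs a thousandfold ratio and will be rare. The HBeAg band lies below the 0.22 PEIU/mL qualitative cut-off, and the protocol quantifies HBeAg only in HBeAg-positive patients, so that case is largely hypothetical. The study is descriptive, and the secondary objective (HBsAg reduction to nadir) does not use these categories.

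Most of this stands, and it limits the point. A reader might infer that the SAP ignores the assay limit altogether, or that full suppression is scored as non-response across all five markers. The documents do not support either reading. The best HBV DNA result, not detected, scores at least 0.60. The HBV DNA result that can reach the lowest category is below LLQ but detected, which section 11 itself classes as target detected. HBsAg loss scores at least 2.30 from the entry minimum. The category label states a size of change; the SAP uses the term non-responder only for seroconversion.

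The reply leaves some gaps:
- HBcrAg has no qualitative summary, and its below-LLQ counts have no assigned table.
- SAP section 2.2.3 names three HBV DNA categories, but the qualitative summary defines two and merges below-LLQ detected with quantifiable results. A fall from 40 IU/mL to below LLQ detected therefore shows in neither that summary nor the decline table.
- The listings of patients who worsened cover only those below LLQ at baseline, who are excluded from this table.

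**Conclusion.** The concern holds as a defect of one table. Two parts follow from the wording alone: 3.0 log has no category, and every increase is labelled a small decline. The only alternative reading of the second is that increases have no category at all.

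The floor effect is narrower. It reaches the lowest category only for low-baseline HBcrAg, HBeAg and HBV DNA below LLQ but detected. For HBsAg it acts only at the top: loss from 25 IU/mL or less cannot be counted as more than 3 log.

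This rests on three assumptions. Day 1 HBsAg is taken to be at least 5 IU/mL, as at screening. HBV RNA is taken as not logged a second time: section 11 exempts it from log transformation in one place and includes it in another. With a second log, a fall from 1.65 to 0.825 would score 0.30 and land in the lowest category. The categories are taken to apply to all five log-scale markers.

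The documents do not give baseline distributions, so the number of affected patients is unknown. No error rate, sample size or primary conclusion changes.

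**What to change.** In SAP section 11 and Table 14.2.4.2.3:

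- Define the top category as a decline of 3 log or more.
- Split the lowest category into 0 to <0.5 log decline and increase from baseline.
- Keep every patient in their log-decline category and add, within each category, a non-exclusive count of those below LLQ at that visit, split into detected and not detected for HBV DNA and HBV RNA. This also gives the below-LLQ counts in the Data Handling Rules a table.

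The below-LLQ row should not override the decline categories. A patient going from HBsAg 10,000 IU/mL to loss has a decline of log10(10,000/0.025) = 5.6 log, and an overriding row would take the deepest responses out of the top category.

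The cost is a wording change, reprogramming of one table and a few extra rows per marker. No new data are needed.
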